8. ETHICAL PRINCIPLE

8.1 Ethical Review

This study will be conducted in accordance with the requirements of the Declaration of Helsinki and relevant national regulations in China. The research protocol complies with applicable laws and regulations and will receive approval from the Ethics Committee prior to implementation. Throughout the research process, the investigators will strictly adhere to the research protocol and standardized operating procedures. If any necessary changes are required to the research plan or informed consent during the study, they must be resubmitted to the Ethics Committee for

review and approval before implementation.

8.2 Informed Consent

Before enrolling each research subject in this study, the researcher staff must provide the subject or their legal representative with a complete, comprehensive, and easy-tounderstand informed consent document, along with an explanation approved by the Ethics Committee, in written form. The researcher must also allow sufficient time for the subject or their legal representative to consider whether to participate in the study. Subjects or their legal representatives may only enter the study after signing the informed consent. During the study period, if new safety information leads to significant changes in the risk/benefit assessment, the subject or their legal representative should be provided with all updated information, and a new informed consent form must be signed.

8.3 Risk Minimisation

In the study, the cardiovascular health surveys, physical examinations, and lab tests for the study participants, will be conducted by trained research staff, which will not pose any risk to the participants. In the questionnaire interview, participants may choose not to answer any questions they prefer to skip. Fingertip blood collection may cause mild pain and subcutaneous bruising; if discomfort arises, participants can seek on-site medical assistance. During the study, the village doctors will provide the participants with guidance on lifestyle modification or medication recommendations that do not introduce additional health risks. If participants have any questions about the study, professional staff will be available to address them. Participants have the right to decline participation or withdraw from the study at any stage without any impact on their medical rights. All the data in this study will be stored at the national coordinating centre and will be kept strictly confidential, and all research staff will receive training in data security. Health monitoring data in the intervention group, such as the step counts and heart rate collected by smart bands, will be uploaded to the Huawei Research Platform and subsequently transferred to the research database.

All research staff, as well as inspectors from relevant government departments or academic management bodies, must obtain authorization from the primary investigators to access the database, which is password-protected. Strict security measures will be implemented to prevent unauthorized personnel from accessing the personal information of study participants, and no staff member shall disclose this information to external parties. The identities and any other personal information of the participants will remain confidential and will not be disclosed in any research report. All expenses incurred for the examination items in this study will be covered by the research sponsor, and participants will not be required to pay any costs. However, the study does not cover treatment expenses incurred by participants for personal medical reasons, transportation subsidies, or any other forms of compensation or remuneration.

8.4 Safety Issues

The interventions in this study do not involve any new drugs or invasive procedures and do not pose risks beyond those associated with routine clinical care. Furthermore, these interventions may help reduce disease risks. Therefore, no special safety monitoring is required for this study. Nevertheless, the study will document all deaths, hospitalizations, and other significant medical events that may be defined as serious adverse events. In addition to monitoring serious adverse events, participants will be asked at each follow-up visit whether they have experienced symptoms of low blood pressure, hypoglycaemia, or sports-related injuries.



TABLES

Table 2. Cardiovascular	risk factors to	be assessed in t	the SMARTER study
	11511 100001 5 00		

Risk factors	Indicators	Warning criteria
10-year risk of ASCVD	Risk (value)	≥10%
	Risk (stratification)	High-risk
1. Hypertension	SBP	≥130 mmHg
	DBP	≥80 mmHg
2. Diabetes	FBG	≥6.1 mmol/L
3. Dyslipidaemia	TC	\geq 5.2 mmol/L
	Non-HDL-C	\geq 3.4 mmol/L
4. Obesity	BMI	Overweight: $\geq 24 \text{ kg/m}^2$, Obesity: $\geq 28 \text{ kg/m}^2$
	Bodyweight	According to the BMI criteria
	Waist circumstance	Males: ≥90 cm, Females: ≥85 cm
5. Smoking	Daily smoking amount	>0
	Heaviness of Smoking Index (HSI)	Heavy dependence
6. Alcohol use	Daily consumption of pure alcohol	≥15g (on average)
7. Physical activity	Total physical activity	<3000 MET-min/wk
	Exercise intensity	No exercise
	Weekly exercise time	Moderate-intensity aerobic activities<150 minutes, or vigorous-intensity aerobic activities<75 minutes
8. Unhealthy diet	Fruit	Less than everyday
	Fresh vegetables	Less than everyday
	Whole grains	Less than everyday
	Bean and bean food	Less than four days per week
	Red meat	Everyday
9. Sleep deprivation	Sleep duration	<6 hours/day (on average)
10. Medication adherence	Self-reported adherence	Intermittent or absent use of medications

Risk factors	Targets	Principles
Hypertension	SBP/DBP	Age<80: <130/80 mmHg; Age≥80: <150/90 mmHg (recommended; allow for adjustment according to the circumstances)
Diabetes	FBG	Participants without a diagnosis of DM: <6.1 mmol/L; DM patients: <7.0 mmol/L
Dyslipidaemia	Non-HDL-C	Age<75, no diagnosis of DM: <3.4 mmol/L; Age<75, DM patients: <2.6 mmol/L; Age ≥75: lipid lowering target should be set under guidance of the physicians in higher-level hospitals
Obesity	Weight loss	BMI<28 kg/m ² : with a body weight at BMI 24 as the target weight, setting the weight loss goal to be achieved in four stages during follow-up; BMI≥28 kg/m ² : setting a 15% of the current body weight as the bodyweight loss goal to be achieved in four stages during follow-up
Smoking	Smoking cessation	Never smokers: no smoking; Current smokers: quitting smoking
Alcohol use	Alcohol reduction	Never drinkers or non-weekly drinkers: no alcohol; Weekly drinkers: limiting the frequency and consumption of alcohol (pure alcohol should not exceed 15g per day on average)
Physical activity	Daily step count; Exercise frequency	Age<60: the daily step count should reach 8000- 10000 per exercise day; Age≥60: the daily step count should reach 6000- 8000 per exercise day; At the first 6 months of the study, it is recommended to exercise at least 3 days per week; at the last 6 months, competent participants are recommended to exercise 5 days per week

Table 3. Principles for Establishing Individualized Health Promotion Goals

1. INTRODUCTION

This Statistical Analysis Plan (SAP) outlines the main statistical analyses to be conducted on the data collected in the Strategy for Cardiovascular Disease Prevention through Tailored Health Management and Its Effectiveness Assessment through a Cluster Randomised Trial in Individuals with Elevated Risk (SMARTER) study, in accordance with the study protocol. It provides an overview of the study, summarizes the key variables that will be analysed, and describes the statistical methods that will be employed in the analyses. The results reported in the papers should follow the methodologies set out here.

The analyses as planned in the SAP will be performed after the completion of the trial. All procedures should be conducted by qualified statisticians, ensuring the integrity and accuracy of the data and the fidelity to the SAP. Any deviations from the SAP should be described and justified in the final report of the trial.

2. STUDY OBJECTIVE

2.1 Objectives

The objective of the SMARTER study is to develop a series of effective, feasible, and sustainable health management strategies led by village doctors in rural China, and assess their effectiveness of these strategies in reducing the 10-year risk for developing atherosclerotic cardiovascular disease (ASCVD) and in managing cardiovascular risk factors in individuals with elevated risk over a 12-month period.

2.2 Assumptions

The null hypothesis to be tested is that the village doctor-led tailored health management will have no effect on 10-year ASCVD risk and risk factor control in individuals with elevated risk.

3. METHODS

3.1 Study Design

The SMARTER study was an open-labelled, cluster-randomized controlled trial. A total of 4533 participants in 127 villages (clusters) were enrolled from five provinces and autonomous regions across China and randomly assigned in a 1:1 ratio to the intervention group and control. Participants in the intervention group received the village doctor-led multifaceted mobile health interventions, and the control group received usual care. Participants in both groups will be followed for 12 months and received follow-up visits every three months, specifically at the 3rd, 6th, 9th, and 12th months. The primary outcome of the study is the mean change in 10-year risk of ASCVD from baseline to 12 months, and the secondary outcomes are the changes in metabolic and lifestyle risk factors from baseline to 12 months.

3.2 Study Population

3.2.1 Inclusion Criteria for villages

- (1) having a village clinic that stocked common cardiovascular drugs;
- (2) having at least one certificated village doctor who has technical school education or above and is willing to participate in the study;

(3) being at least 2 km away from other participating villages.

3.2.2 Inclusion Criteria for Participants

Individuals were considered eligible if they met all the following criteria:

(1) aged 35 or above;

(2) 10-year risk of ASCVD \geq 10% based on the Prediction for ASCVD Risk in China (China-PAR) model;

- (3) owning a smartphone and being able to use applications (apps);
- (4) contracting with the local village doctor for family doctor service;

(5) being willing to participate and sign the informed consent.

3.2.3 Exclusion Criteria for Participants

Individuals were excluded if they met any of the following conditions:

(1) a history of myocardial infarction (MI), stroke, heart failure, severe arrhythmia, or having received percutaneous coronary intervention (PCI) or coronary artery by-pass grafting operation (CABG);

- (2) severe illnesses, such as cancer, severe hepatic or renal dysfunction;
- (3) pregnant or lactational women, or those planning to conceive in 12 months;
- (4) cognitive impairments, communication issues, or limitations in activities.

3.3 Randomisation and Blinding

The group assignment was conducted by a central randomisation system based on minimisation algorithm. The villages served as the units of randomisation. The assignment was stratified by county, and was conducted after all participants within each county had been recruited and baseline survey data had been collected. Factors that were balanced between the comparison groups include participants' age, systolic blood pressure, and 10-year risk of ASCVD, as well as the education attainment of the village doctor. Random numbers were generated by an independent statistician using a computer. A random element of 0.9 were introduced to enhance unpredictability in the allocation process.

Due to the nature of the cluster design and the intervention programme, the village doctors and the study participants were aware of their group allocation. However, the allocation will be concealed from the study statisticians.

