3.2.1.1 Provinces and autonomous regions, counties and villages

Provinces and autonomous regions – The study choose 5 provinces and autonomous regions that are willing to participate (Henan Province, Shandong Province, Liaoning Province, Ningxia Hui Autonomous Region, Jiangxi Province).

Counties – At least 12 counties will be selected from the collaborating provinces and autonomous regions to provide diversity in geographic distribution, socioeconomic development, and lifestyle patterns.

Villages – At least 120 villages will be selected from the counties based on their population size and stability, as well as the capacity of village clinics and the qualifications of village doctors. The eligibility criteria for villages will be as follows:

(1) having a village clinic that stocked common cardiovascular drugs;

(2) having at least one certificated village doctor who has technical school education or above and is willing to participate in the study;

(3) being at least 2 km away from other participating villages.

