6.3 Analysis of Primary Outcomes

The primary outcome of the trial is the mean changes in 10-year risk of ASCVD based on the China-PAR model from baseline to the 12 months. Linear mixed effects model will be used to compare the primary outcome between the intervention group and the control group. The dependent variable is the change in 10-year risk of ASCVD of the participants from baseline to the 12-month, and the independent variable is the study group. Villages will be adjusted in the model as a random effect. The net difference between the two groups was assessed by the model, with multivariable adjustment by baseline covariates including age, sex, education, occupation, annual household income, marital status, and social medical insurance.

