APPENDIX 4:

ANALYSIS CODE FOR THE STUDY

* Compare Baseline Characteristics; * continuous variables; proc means data=smarter data mean std; var IS age SBP0 DBP0 GLU0 NHDL0 waist0 BMI0 risk0 risk lifetime 0; by group; run; * categorical variables; proc freq data=smarter data; tables male pd education pd labor pd income pd married pd insure smk daily 0 PA 1t3000 0; by group; run; * Evaluation of Research Outcomes; data fu4 data; set smarter data; if risk4^=.; run; proc means data=fu4 data n mean std; var risk0 risk4 risk lifetime 0 risk lifetime 4 SBP0 SBP4 DBP0 DBP4 GLU0 GLU4 NHDL0 NHDL4; by group; run; proc freq data=fu4 data; tables obesity 0 obesity 4 smk daily 0 smk daily 4 PA lt3000 0 PA lt3000 4 LTPA0 LTPA4; by group; run; proc means data=fu4 data n mean clm; var risk4_change risk_lifetime4_change SBP4_change DBP4_change GLU4_change NHDL4 change; by group; run;

* model for continuous variables (eg.10-y ASCVD risk);

proc glimmix data=fu4_data;

class village_id group(ref='2') male education_high_above Last_year_income_lt_10k
occupation_farmer marriage_yes insure_yes vc_risk_grp vc_sbp_grp vc_age_grp
doctor_college_above;
model risk4_change=group risk0 IS_age male education_high_above
Last_year_income_lt_10k occupation_farmer marriage_yes insure_yes vc_risk_grp
vc_sbp_grp vc_age_grp doctor_college_above
/solution dist=normal link=identity ddfm=bw cl ;
random int/subject=village_id type=un;
run;

* model for categorical variables (eg.smk daily);

proc glimmix data=fu4_data;

class village_id group(ref='2') male education_high_above Last_year_income_lt_10k
occupation_farmer marriage_yes insure_yes smk_daily_0 vc_risk_grp vc_sbp_grp
vc_age_grp doctor_college_above;
model smk_daily_4(event="1") =group smk_daily_0 IS_age male education_high_above
Last_year_income_lt_10k occupation_farmer marriage_yes insure_yes vc_risk_grp
vc_sbp_grp vc_age_grp doctor_college_above/solution dist=binary link=logit ddfm=bw cl;
random int/solution subject=village_id type=un;
ods output ParameterEstimates=Coefficients_smk;
run;

data coefficients_smk; set coefficients_smk; if effect~='Intercept' then do; PA_OR=exp(Estimate); PA_OR_L=exp(Estimate-1.96*stderr); PA_OR_U=exp(Estimate+1.96*stderr); PA_OR_95CI=compress(put(PA_OR,4.2))||"("||compress(put(PA_OR_L,4.2))||","||compress(p ut(PA_OR_U,4.2))||")"; end; run; * Subgroup Analysis;

* eg.sex: male/female;

data male; set fu4_data; if male=1; run; data female; set fu4_data; if male=0; run;

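### County, the stratification factor, is missing from the analysis models; standard errors for the continuous outcomes are probably conservative, by an amount the documents do not fix

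*Combined protocol and SAP*

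**What the plan says.** Protocol 3.2.2 and SAP 3.3 describe the same allocation: villages randomised by minimisation, stratified by county. The SAP wording is "The assignment was stratified by county, and was conducted after all participants within each county had been recruited". On the minimisation factors, SAP 3.3 says "Factors that were balanced between the comparison groups include participants' age, systolic blood pressure, and 10-year risk of ASCVD", and it adds the village doctor's education. Protocol 3.2.1.1 gives the number of counties only as a minimum ("At least 12 counties will be selected from the collaborating provinces and autonomous regions") and says they were chosen "to provide diversity in geographic distribution, socioeconomic development, and lifestyle patterns".

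For the primary analysis, SAP 6.3 says "Villages will be adjusted in the model as a random effect", "with multivariable adjustment by baseline covariates including age, sex, education, occupation, annual household income, marital status, and social medical insurance". SAP 6.4 repeats this for the secondary outcomes, and 6.5 adds no further term for subgroups. In Appendix 4 the random part is "random int/subject=village_id type=un" and the fixed part begins "model risk4_change=group risk0 IS_age male education_high_above". It goes on to village-level groups for risk, SBP and age and to the doctor's education. No `CLASS`, `MODEL` or `RANDOM` statement contains county. The footnotes to Table S5, Fig S4 and Table S6(a) list village, the four minimisation factors and the personal covariates, again without county. No reason for leaving it out is given.

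**The concern.** A factor used to restrict randomisation normally belongs in the analysis. Here the code and footnotes adjust for all four minimisation factors but omit the one stratification factor, so the omission does not look like a general choice against adjusting for allocation factors.

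When villages are allocated within county, county differences largely cancel from the difference between arms. If the model has only a village random intercept, those differences still enter the estimated village variance and so the standard error of the arm effect. The expected result is coverage above 95% and lost precision, not false positive findings. Counties were chosen to differ, so a county share of exactly zero would be surprising, but the documents give no estimate of it.

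**Working it through.** **Inputs.** From the SAP sample size section: difference 1.0 percentage point, SD 6.0, ICC 0.06 (actual), 10% loss, 4533 participants in 127 villages, stated power 88%. From Table S6(a): −1.88 (−2.57 to −1.19). Assumed: 12 counties, close to 1:1 allocation within each county, and a share *f* of between-village variance that lies between counties.

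**1. The SAP's own figure.** Participants per village after loss: m = 4533 × 0.9 / 127 = 32.1. Design effect: 1 + (32.1 − 1) × 0.06 = 2.87. Effective n per arm: 2040 / 2.87 = 711. SE = 6.0 × √(2/711) = 0.318. Power = Φ(1/0.318 − 1.96) = 88.2%. The stated 88% is reproduced, with no credit for stratification.

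**2. With county in the model.** Between-village variance: b = 0.06 × 36 = 2.16. Within-village part of a village mean: w = 0.94 × 36 / 32.1 = 1.05. Then SE = √[(4/127) × ((1 − f) × b + w)].

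The last two columns come from a simulation with allocation balanced within county: 6000 runs per setting, village means analysed, and the county degrees of freedom charged.

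| f | SE with county | Power with county | Width ratio, without / with county | Coverage without county |
|---|---|---|---|---|
| 0% | 0.318 | 88.2% | 0.997 | 95.2% |
| 10% | 0.307 | 90.2% | 1.03 | 95.5% |
| 25% | 0.290 | 93.1% | 1.09 | 96.5% |
| 50% | 0.259 | 97.1% | 1.21 | 97.8% |

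The gain in power is smaller than a comparison with 88.2% suggests. When f is above zero, the estimate from the village-only model also varies less than its SE implies. Simulated power was 88.5%, 89.5%, 91.0% and 92.9% without county, against 88.6%, 90.1%, 93.4% and 97.2% with it.

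**3. The visible primary interval.** Half-width (2.57 − 1.19)/2 = 0.69, so SE = 0.69/1.96 = 0.352. Assume a within-village SD of 6.0 and 4434/127 = 34.9 analysed per village. The implied between-village variance after adjustment is 0.352² × 127/4 − 36/34.9 = 2.90. Adding county would then give about −2.50 to −1.26 at f = 25% and −2.43 to −1.33 at f = 50%. Zero is excluded with or without county.

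**4. The two outcomes with P above 0.05 in Table S6(a).** At ICC 0.06 and 34.9 per village, the village part of the variance is 0.06 × 34.9 / 3.03 = 0.69. At f = 50% the SE factor is √(1 − 0.5 × 0.69) = 0.809. With the estimates held fixed:

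- Non-HDL-C: −0.06 (−0.19 to 0.08) becomes about −0.17 to 0.05.
- Obesity: OR 0.83 (0.65 to 1.05) has a log-odds SE of 0.122, which becomes 0.099. z rises from 1.52 to 1.88 and P is about 0.06. This is an illustration only, because the factor is derived for linear models.

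**The case against.** A reader might infer that every treatment-effect interval in the trial is too wide. The documents do not support that, for four reasons.

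- Widening needs residual between-county variance in the particular outcome, and none is reported. At f = 0 the village-only interval was the wider one in only about 40% of simulated trials.
- The code already adjusts for the baseline value, village-level risk, SBP and age groups, and the doctor's education, which may absorb part of the county variation. Step 3 suggests that much village-level variance remains after adjustment: 2.90 of 3.94, or 74%, under its assumptions. It does not show how much of that is county.
- The binary outcomes use logistic mixed models and MACE a Cox frailty model. Adding county there can move the estimate as well as its SE.
- If the treatment effect itself varies by county, intervals need not be too wide. In one assumed scenario (f = 25%, SD of the county effects 0.7 points), coverage of the average effect was 92.4% without county and 90.0% with it. That is a separate question, but it shows that the county term does not cure everything.

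A second tempting inference is that the omission explains why power was 88% and not 90%. It does not. The sample size calculation claims no gain from stratification. With 4533 participants, 127 villages and 10% loss, power is 94.4% at the planning ICC of 0.04 and 88.2% at 0.06, so the fall comes from the ICC. Including county might offset it.

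These objections limit the size and reach of the point. They do not explain the omission.

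**Conclusion.** The omission is certain: county restricted the randomisation and is absent from the SAP models, the code and the listed adjustments. For the continuous outcomes the likely direction is conservative standard errors. The amount is unknown, from nothing at f = 0 to about 21% in interval width at f = 50%, given 12 counties, ICC 0.06, balanced allocation within county and a treatment effect that is constant across counties. For the odds ratios and the MACE hazard ratio, neither direction nor size is determined.

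The primary conclusion does not change. The only primary interval in these documents comes from the sensitivity analysis that excludes participants with MACEs, and the main-analysis interval is not shown. Neither result above P = 0.05 in that table crosses the threshold at f = 50% with estimates held fixed. What is at stake is precision and agreement between design and analysis.

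**What to change.** Add county as a fixed effect (in `CLASS` and `MODEL`) to the linear mixed models for the primary and continuous secondary outcomes and to the interaction models, and state it in SAP 6.3 to 6.5. Add it to the binary-outcome models, to small subgroups and to the MACE model only where numbers per county allow. The lower-income subgroup has 358 + 347 participants, and the MACE event count is not visible here. Give the actual number of counties.

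As the trial is complete, report the county-adjusted results either as a deviation, described and justified as SAP section 1 requires, or as a labelled sensitivity analysis beside the existing model. If county stays out, give the reason.

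Cost: one term per model and (number of counties − 1) between-village degrees of freedom, which is 11 of roughly 120 if there are 12 counties. No new data are needed, since county was recorded in order to stratify. If counties do not differ, the loss of precision in the linear models is negligible (width ratio 0.997).
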